Describe the purpose, specific aims or objectives and specify the hypotheses or research questions to be studied:

The purpose of this research is to address gaps in understanding of the mechanisms of AAI and how these mechanisms may differ across special populations hinder progress in the application of AAI, and limit the acceptability and availability of this integrative health care practice. Our bio-social mechanistic hypothesis contends that dogs elicit physiological responses related to arousal of EF systems, thereby enhancing response to treatments. Furthermore, candidate individual differences potentially mediate outcomes. This work will explore these hypotheses; 1) we suspect AAI will result in enhanced social-behavioral outcomes and improved diurnal patterns of HPA and ANS activity for these children and 2) we suspect acute physiological responses to AAI (markers of HPA & ANS) and social interaction quality (child/child and child/dog) will mediate main outcomes.

Specific Aims Specific Aim 1: To replicate previous findings that social-behavioral outcomes are improved for children with ADHD when they participate in an 8- 10 week manualized AAI with therapy dogs. Specific Aim 2: To explore if diurnal patterns of physiological markers of Hypothalamic Pituitary Adrenal axis (HPA) activity (salivary cortisol; Cort and uric acid; sUA) and Autonomic Nervous System (ANS) activity (heart-rate variability; HRV, and salivary alpha-amylase; sAA) are improved over time for children with ADHD in response to an 8- 10 week manualized AAI with therapy dogs. Specific Aim 3: To explore if potential individual differences in children with ADHD are manifested during intervention sessions and if these differences mediate primary and exploratory main outcomes from an 8- 10 week manualized AAI with therapy dogs. Specific individual differences explored include; acute physiological responses during intervention sessions as measured by markers of HPA & ANS activation (Cort, sUA, sAA, & HRV) and the quality of social interaction (child/child and child/animal) during sessions.

Provide the scientific or scholarly rationale for the research and describe the relevant background information and the specific gaps in current knowledge that this study intends to address:

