This project explores physiological mechanisms thought to underlie the positive effects of AAI for children with ADHD and posits that interaction with dogs during treatment improves social behavioral and physiological outcomes and that individual differences in bio-markers and interaction style mediate outcomes for this group. **Rationale & Background** Despite decades of research aimed to optimize outcomes for children with ADHD, the condition remains a significant public health problem adversely impacting individuals, families and schools. The annual cost of ADHD is estimated at \$266 billion (Doshi et al., 2012). Pharmacotherapy (e.g., methylphenidate) is the mainstay of traditional medical intervention for ADHD, but treatment failures are common (Caye, Swanson, Coghill, & Rohde, 2018; Schneider & Ennenbach, 2014; Swanson et al, 2018), and affected children often require medications during what are now recognized as critical periods of growth and development. It is not surprising that parents find alternative therapies, including Animal Assisted Intervention (AAI), to be more acceptable than medication (Rabbit, Kazdin, & Hong, 2014). Our research found AAI to be effective in reducing ADHD symptoms and improving social skills and self-perception ([name] et al., 2015; [name] et al., 2018a, [name] et al., 2018b). **Gaps in Current Knowledge** While we demonstrated the effectiveness of AAI for this group, the underlying mechanisms of these effects is unknown; a critical gap in our developing body of evidence for AAI needed to increase the acceptability and accessibility of this integrative health care strategy. The research proposed in this application will break ground in this nascent area and contribute to the rapidly developing discipline of HAI research by (1) contributing to our understanding of bio-social mechanisms which may underlie outcomes, (2) identifying individual responses thought to mediate outcomes and (3) informing the development of future large scale, multi-site trials aimed to informing best practices for delivering AAI in special pediatric populations and improving accessibility to this practice.

Provide relevant preliminary data (animal and/or human):

N/A

Describe the primary outcome variable(s), secondary outcome variables, and predictors and/or comparison groups as appropriate for the stated study objectives/specific aims:

N/A

List up to ten relevant references/articles to support the rationale for the research:

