
both treatment conditions and we will b) ascertain the quality of in-session social relationships (child-child) across both treatment conditions as well as the quality of in-session child animal interaction (child-dog) during the AAI sessions (observed child/child & child/dog interaction) at three (3) time points across the 10-week study intervention period (weeks 1, 5, & 10). The acute response and interaction quality measures from each of the three sessions will then be correlated with the degree of change in the primary main outcomes. (e.g., pre-post change in ADHD symptoms, social skills, regulation) and the exploratory main outcomes (e.g., pre-post change in diurnal HPA activity and ANS activity) to examine the potential mediation of individual differences on response to AAI with therapy dogs for children with ADHD. Here we provide an example of one mediation analysis for treatment group (AAI vs Control) as the primary predictor, salivary cortisol response slope at session 5 the potential mediator, and behavioral change (pre-post change) the outcome: First, cortisol response slope² means will be compared between the groups (the mediator must be related to the predictor). If significant, then the relationship between cortisol response slope², and behavioral change will be evaluated for a significant correlation/slope (the mediator must be related to the outcome). Finally a model will be run with both treatment group and cortisol response slope² predicting behavioral change. If the relationship between treatment group and behavioral change is reduced compared to the primary analysis (i.e., with treatment group alone), saliva cortisol response² is interpreted as providing a mediated effect. To obtain estimates of the size and significance of the indirect effects, bootstrapping procedures as described by Shrout and Bolger (2002) will be implemented. Due to the fact that bootstrapping procedures are still limited in the case of multilevel models, an approximation of the Sobel test will also be performed, along with Monte Carlo estimation of confidence intervals but because this aim is exploratory and this is not a fully powered study, results presented will include descriptive and confidence intervals.

Describe the statistical method(s) that will be used to analyze the primary outcome(s) or endpoints:

see previous section

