If appropriate describe secondary or post hoc analyses of primary outcome(s) or other exploratory analysis and if necessary, provide a breakdown of the methods used per outcome or endpoint:

Statistical Method to Inform Randomization Bias: Intent to treat bias. To establish equivalence of randomly assigned groups pre-intervention, t-tests will be performed on outcome measures comparing the groups. Means and standard deviations will be obtained and effect sizes calculated. Demographic profiles will be obtained and bivariate significant tests performed to assess the balance expected with randomization. Cohort effects on outcome as well as participation rates will be evaluated to assess any bias related to location, calendar time, or other session characteristics. Participation rates across the intervention will be tracked and compared between the randomized groups. In the spirit of the intent to treat principle (White, Carpenter, and Horton 2012) every effort will be made to conduct follow-up assessments on all randomized participants. Withdrawals will be documented with reason provided. In addition, multi-level modeling allows all cases to remain in a repeated measures model and will be done as a sensitivity analyses to primary analyses done on individuals with at least one follow-up point.

Sample Size Determination: Explain how the overall target sample size was determined (e.g., power analysis; precision estimation), providing justification of the effect size for the primary outcome based on preliminary data, current knowledge/literature and/or cost consideration; if appropriate, provide sample size justification for secondary outcomes. Power analysis should (at least) match the primary outcome/endpoint:

Sample Size. This exploratory study will employ a parallel-group randomized clinical trial design in which 48 participants will be randomly allocated to one of two (2) treatment/intervention groups (AAI and Control) delivered across four (4) cohorts in two (2) waves over the span of two (2) years ($n = 12$ per parallel ten-week cohort) in efforts to inform the specific aims of the study.

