Power & Expected Effect Size. Sample size analysis was conducted for randomized controlled design, using SAS PROC power. For the primary analysis of the main outcome domain (Aim 1: ADHD Behavior) with type I error rate of .05 was implemented for a repeated measures analysis evaluating group main effect, treatment main effect, as well as the group*treatment interaction. Effect size estimates from the authors' previous parallel-group randomized study of HAI demonstrated large AAI vs control effect size for problem behaviors (.86) and moderate effects on inattention (.45) ([name] et al., 2018a). For Aim 1, with a projected analysis of $n=48$, this exploratory study will exceed 90% power to detect effect sizes of .19 and above. At a level of 80% power, the minimum detectable effect was determined to be .21. For Aim 2, $n = 48$ will, for each of the two primary physiological outcome domains (Aim 2: Diurnal Pattern Hypothalamic Pituitary Adrenal axis activity; HPA and Autonomic Nervous System activity; ANS), a multilevel model will be constructed to assess pre-post intervention change, post-follow up change, group differences at each assessment, and group differences in degree of change. Models will account for within-subject correlation and within-cohort correlation. Four (4) cohorts of 13 participants each will be recruited for a total enrolled target sample size of 52 families over Years 1 and 2, accounting for an anticipated attrition rate of about 8% which is based on our recently completed study of AAI with ADHD ([name], et al., 2018a) in efforts to yield a total sample of 48.

Research Procedures

Provide a detailed chronological description of the clinical or treatment plan:

See Study Design

List all procedures involving the use and/or collection of photographs, or audio/video recording:
Facial image will be in video or photo Participants' first names may be collected or recorded in either video or audio recording

Specify the total duration of a subject's participation in the study and clearly outline the duration of participation for each study visit and sub-study, as applicable:

See Study Design

List data collection tools (e.g., measures, questionnaires, observational tool) below by clicking the 'Add Line' button. Include additional rows for study instruments, as needed:

The 'Columns' button allows you to display or hide columns in the Study Instrument List.

Name of Tool:

The Child's Sleep Habits Questionnaire (Owens, Spirito, & McGuinn 2000)

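### Aim 3's mediation steps can label a marker a mediator when AAI merely shifts it; the planned confidence interval for the indirect effect should decide

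*Combined protocol and SAP*

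**What the plan says.** The mediation method is in Statistical Considerations, under Specific Aim 3. It is given as one worked example: treatment group as predictor, salivary cortisol response slope at session 5 as mediator, and pre-post behavioural change as outcome. The steps are:

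1. Compare marker means between groups.
2. If they differ significantly, look for a significant correlation or slope between marker and outcome change. No adjustment for arm is mentioned.
3. Fit group and marker together. "If the relationship between treatment group and behavioral change is reduced compared to the primary analysis (i.e., with treatment group alone"), the marker "is interpreted as providing a mediated effect".

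Bootstrapping then follows, "To obtain estimates of the size and significance of the indirect effects", together with an approximate Sobel test and Monte Carlo intervals. The text says that results will include descriptives and confidence intervals because the aim is exploratory and not fully powered. It does not say that the label depends on the interval, or what happens if the two disagree.

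The same section plans to observe "the quality of in-session child animal interaction (child-dog) during the AAI sessions". The hypotheses in the purpose and aims section state that "social interaction quality (child/child and child/dog) will mediate main outcomes".

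**The concern.** The study hypothesises that AAI changes both physiology and behaviour. When arm shifts both, the two are correlated in the pooled sample even if the marker has no effect on behaviour. Step 2 can therefore be passed through arm alone. Step 3 ought to catch this, but it asks only whether one estimate is smaller than another.

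Child-dog interaction has a separate problem. It has no control-arm values, so step 1 cannot be computed and there is no AAI-versus-Control indirect effect to estimate.

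Mechanism is the stated purpose of the study, and the rationale lists "informing the development of future large scale, multi-site trials" among its contributions. A marker that AAI shifts without any bearing on behaviour could be carried into those trials as a mechanism.

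**Working it through.** **Inputs**
- Sample size: "48 participants will be randomly allocated to one of two (2) treatment/intervention groups (AAI and Control") (Sample Size section). The ratio is not stated, so 24 per arm is assumed. The enrolment target of 52 is consistent with this: 52 × 0.92 = 47.8 after about 8% attrition.
- Outcome effects: "large AAI vs control effect size for problem behaviors (.86) and moderate effects on inattention (.45") (Power & Expected Effect Size), treated as standardised differences in change scores.
- Arm effect on a marker: none is given. Assumed range 0 to 1.5 SD.
- Significance level: 0.05 is stated for Aim 1 only. Two-sided 0.05 is assumed for the Aim 3 steps.

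The plan gives no error rate or power for the Aim 3 steps, so there is no figure of its own to reproduce.

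**Why step 2 can be passed through arm.** Let M = a·T + e and Y = c·T + e, with unit residual SD, equal arms and no effect of M on Y. The pooled correlation is (ac/4) / √[(1 + a²/4)(1 + c²/4)].
- a = c = 0.45: 0.0506 / 1.0506 = 0.05
- a = c = 0.86: 0.1849 / 1.1849 = 0.16
- a = 1.5, c = 0.86: 0.3225 / √(1.5625 × 1.1849) = 0.24

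With n = 48, significance needs |r| of about 0.28. The shared arm effect brings the correlation part of the way there, and sampling error can do the rest.

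**Why step 3 rarely stops it.** In least squares, the adjusted group effect equals the unadjusted effect minus â·b̂, where b̂ is the marker coefficient with arm in the model. The effect is reduced whenever â·b̂ has the same sign as the unadjusted effect and is less than twice its size. For an inert marker b̂ is symmetric about zero, so this happens in 43–50% of all trials. Trials that have passed steps 1 and 2 are mostly those where b̂ has fallen in the favourable direction.

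**Simulation** (20,000 trials per scenario, inert marker). The interval is a 95% Monte Carlo interval for a·b, with b estimated with arm in the model (4,000 draws).

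| Marker shift (SD) | Outcome effect (SD) | Written steps declare mediation | Interval excludes zero | Step 3 met, given steps 1 and 2 passed |
|---|---|---|---|---|
| 0.45 | 0.45 | 2.3% | 1.4% | 90.0% |
| 0.45 | 0.86 | 5.3% | 1.5% | 98.9% |
| 0.86 | 0.45 | 7.4% | 4.2% | 93.4% |
| 0.86 | 0.86 | 16.8% | 4.1% | 96.6% |
| 1.0 | 0.86 | 20.9% | 4.6% | 95.6% |
| 1.5 | 0.86 | 32.7% | 5.9% | 85.9% |
| 0 | 0.86 | 0.7% | 0.2% | – |
| 0.86 | 0 | 2.7% | 3.9% | – |

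Where AAI moves both, the marker's arm-adjusted coefficient is non-significant in 73–92% of the false declarations.

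A smaller run with the percentile bootstrap (2,000 trials, 1,000 resamples) agrees. At 0.86/0.86 the steps give 16.2% and the bootstrap 4.6%; at 1.2/0.86 they give 25.7% and 5.8%.

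**Real mediator** (b = 0.5, direct effect 0.4). Detection by the steps versus the interval is 31.7% vs 30.0% at a = 0.45, 37.6% vs 35.5% at a = 0.5, and 80.4% vs 75.1% at a = 0.86.

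**The case against.** The strongest reply is that the plan already contains the remedy. The bootstrap, Sobel and Monte Carlo results come straight after the label and will be reported beside it, the aim is declared exploratory, and the three steps are only an example. Step 2 is silent on arm adjustment and does not exclude it. The high error rates also need marker shifts of 0.86 SD or more together with the larger outcome effect, and nothing in the documents supports 1.0 or 1.5 SD. At a 0.45 SD marker shift the rate is 2.3–5.3%.

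These points limit the weight of the concern but do not remove it. The example is the only mediation procedure given, and no sentence lets the interval decide.

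Three further points stand:
- The steps need not be discarded. Requiring both the steps and the interval gave about 2–3% false labels where the marker shift was 0.86 SD or more and AAI also moved the outcome. Where AAI moves the marker only, the interval alone is slightly worse than the steps (3.9% vs 2.7%).
- The interval does not cure confounding. If an unmeasured factor gives an inert marker a within-arm correlation of 0.3 with the outcome, the bootstrap interval excludes zero in about 48% of trials at a 0.86 SD shift on both (84% at a correlation of 0.5).
- The figures are for one marker, session and outcome. The plan has several of each and no multiplicity rule for Aim 3. Within-cohort correlation was not simulated.

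On child-dog interaction, the planned correlation with outcome change is close to a within-AAI association already. The fault lies in calling it mediation.

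**Conclusion.** The concern holds. As written, the steps can call a marker a mediator because AAI shifts it, and the planned interval has no stated authority over that label. The excess arises when AAI moves both marker and behaviour. It is negligible at 0.45 SD on both, about 17% at 0.86 SD on both, and about a third at a 1.5 SD marker shift with a 0.86 SD outcome effect. These sizes rest on assumed marker shifts, 24 per arm, normal errors and two-sided 0.05. The steps are least reliable when AAI works best, which is when a mechanism claim is most likely to be made. The child-dog point needs no assumption: without control-arm values it cannot mediate the arm contrast. Aim 1 is unaffected. This should be corrected, but it concerns interpretation of an exploratory aim.

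**What to change.** Remove the shrinkage criterion and state:

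> For each mediator measured in both arms, the mediator-to-outcome path is estimated with treatment group in the model. Mediation is interpreted only from the bootstrap or Monte Carlo 95% confidence interval for the indirect effect.

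Steps 1 and 2 may stay as descriptive results. Take child-dog interaction out of the mediators of AAI versus Control, and report its association with outcome change within the AAI arm (about 24 children), descriptively with a confidence interval. A sentence noting that a mechanism reading also assumes no unmeasured marker-outcome confounding would be a useful addition.

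The cost is wording only. The intervals are already planned, and the renewal's progress report says no data had been analysed at that point. Somewhat fewer real mediators will be labelled (30–75% detected instead of 32–80% in the scenarios above), and most intervals will be wide at n = 48.

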Statistical Method per Outcome Specific Aim 1: Replicate Previous Favorable Behavioral Response to AAI Primary Main Outcome: Behavior responses. This parallel-group randomized design and will utilize a multi-method and multi-source assessment protocol. The assessment protocol will use a repeated-measure within-subject design, gathering main outcomes at three time points to assess the efficacy of AAI on outcomes for children with ADHD who are participating in a short-term intervention with or without the assistance of certified therapy dogs (see Figure 1). Our previous research indicated that after just 2 weeks of intervention, participants in the AAI condition showed significantly greater improvement in symptoms compared to control participants and that these gains were maximized by 10 weeks and then maintained at 6 weeks post intervention ([name] et al., 2018a), suggesting that 10 weeks is an ideal duration of treatment to detect significant benefits from AAI with dogs. Outcomes from AAI utilizing a manualized treatment with therapy dogs (AAI) will be compared to standard of care evidence-based psychosocial treatment at usual (control). Specific Aim 2: Determine Physiological Response over time to AAI for children with ADHD. Exploratory Main Outcome: Diurnal HPA and ANS responses. To determine if children with ADHD present with measurable changes in physiological responses to a short-term AAI (10 weeks) on measures of HPA and ANS we will gather candidate salivary analytes (salivary cortisol, uric acid, and alpha-amylase; Cort, sUA, sAA, respectively) and measures of cardiac rhythm, (heart rate variability; HRV) prior to and post intervention for children participating in both treatment conditions before, immediately after, and upon treatment follow up. Specifically, for each domain we will ascertain changes in diurnal patterns of candidate physiological measures utilizing a linear, repeated measures design gathered across three (3) points in time; establishing individual baseline patterns, end of treatment patterns, and then patterns at 6 weeks post-treatment. Specific Aim 3; Explore Individual Differences as potential mediators of response to AAI in children with ADHD. Secondary Outcome Exploratory Mediator Analysis; In the proposed study, we will explore how children's individual (a) acute physiological responses during intervention sessions and their individual (b) social interaction quality during intervention sessions may play a role in each of the Main Outcomes. Specifically, we will a) ascertain acute HPA activity (as measured by Cort, and sUA) and acute ANS activity (as measured by HRV and sAA) during intervention sessions across

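### Aim 3 judges mediation by a drop against the primary analysis, which may rest on other children and another outcome, so the drop need not equal the indirect effect

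*Combined protocol and SAP*

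**What the plan says.** All references are to the combined protocol and SAP.

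- **Mediation model (Statistical Considerations, Specific Aim 3).** The worked example takes "salivary cortisol response slope at session 5 the potential mediator, and behavioral change (pre-post change) the outcome". In-session measures are taken "at three (3) time points across the 10-week study intervention period (weeks 1, 5, & 10").
- **Order of steps (same place).** Two significance conditions come first: "the mediator must be related to the predictor" and "the mediator must be related to the outcome". A model with both treatment group and mediator is then fitted. Mediation is interpreted "If the relationship between treatment group and behavioral change is reduced compared to the primary analysis (i.e., with treatment group alone").
- **Indirect effect (same place).** Its size is also to be estimated by bootstrap, with a Sobel approximation and Monte Carlo intervals. The aim is called exploratory and short of full power, and results are to be descriptive with confidence intervals.
- **Primary analysis.** Specific Aim 1 describes "gathering main outcomes at three time points to assess the efficacy of AAI". The paragraph on power describes "a repeated measures analysis evaluating group main effect, treatment main effect, as well as the group*treatment interaction". The paragraph on intent to treat, under secondary and post hoc analyses, refers to "primary analyses done on individuals with at least one follow-up point".

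Nowhere does the plan require the two compared models to use the same children or the same outcome, or say how a missing session measure is handled.

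**The concern.** The logic of the last step is that the total effect minus the direct effect is the part carried by the mediator. For linear models this is exact only if both effects come from the same children, the same outcome and the same covariates.

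The plan aims to assess every randomised child at follow-up, including those who stop attending. A child without a session-5 sample who is assessed later therefore counts in the primary analysis but cannot enter the mediator-adjusted model. So does a child who misses the post visit but attends the later follow-up. If such children differ in outcome, and differ by arm, the treatment coefficient moves between models for reasons unrelated to cortisol, amylase, uric acid, heart-rate variability or interaction quality.

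At stake is the mechanistic reading of Aim 3. The descriptive drop could point to a mediator that does nothing, hide one that works, or disagree in size or sign with the bootstrapped indirect effect. The plan does not say which of the two governs.

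**Working it through.** **1. The plan's own figure.** The only stated number on who enters the models is enrolment of 52 to yield 48 at about 8% attrition. 48/0.92 = 52.2, and 52 × 0.92 = 47.8, with 4 cohorts × 13 = 52. The figure reproduces to within rounding. The 8% is used up in going from 52 to 48, so it is not a rate of missing session measures among the 48. The documents give no such rate.

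**2. What each model needs.**

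| | Primary analysis | Mediator-adjusted model |
|---|---|---|
| Outcome | repeated measures, three time points | pre-post change |
| Session measure | not needed | needed (session 5 in the example) |
| Post visit | not needed if the later follow-up exists | needed |
| Child with no follow-up at all | out | out |

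**3. Decomposition.** Let c_P be the group effect in the primary analysis. In the mediation set, let c_M be the effect without the mediator and c'_M the effect with it. Then

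c_P − c'_M = (c_P − c_M) + (c_M − c'_M).

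The second bracket equals the indirect effect. The first reflects only the change of children and outcome, and the plan's rule counts it as mediation.

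**4. Size of the first bracket, by hand.** Assumptions: 24 per arm, outcome SD 1, true effect .45 (the plan's inattention figure).
- *Random gaps, same outcome:* SD = √(4/n − 4/48). With 44 of 48 retained it is 0.087; with 38 retained, 0.148. The mean is zero, so rises are as likely as falls.
- *Gaps related to outcome:* if 4 of 24 controls are absent from the mediation set and average 0.5 SD worse than the other 20, the effect falls by 0.5 × 4/24 = 0.083, and 0.083/0.45 = 19%. If the 4 are in the AAI arm instead, the effect rises by the same amount and masks mediation.
- *Different outcome:* suppose the primary effect averages post and follow-up. If the follow-up effect is 1.3 times the post effect, the shift is 0.45 × (1 + 1.3)/2 − 0.45 = 0.07; at 0.7 times it is −0.07.

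**5. Simulation with no mediation.** There were 8,000 runs per scenario: 52 children, 1:1, 8% withdrawal, effect .45, a group difference in the mediator of 0.8 SD, no mediator effect on outcome, and post/follow-up residual correlation 0.7. About 47.8 children enter the primary model, and about 43 (10% gaps) or 38 (20% gaps) the mediation model. In the outcome-related rows, better responders in the AAI arm miss more.

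| Missing session measure | Mean drop as written (SD) | Drop of at least 20% of effect, as written | Same, same children and outcome |
|---|---|---|---|
| 10% random | 0.00 (0.20) | 31% | 22% |
| 20% random | 0.00 (0.24) | 34% | 23% |
| 10% outcome-related | 0.08 (0.20) | 48% | 22% |
| 20% outcome-related | 0.20 (0.24) | 68% | 23% |

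On the same children and outcome the mean drop is 0.00 throughout, with SD 0.14 to 0.15. The 20% threshold is only a yardstick; the plan sets no minimum drop.

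**6. After the two significance steps.** In the four scenarios above, both steps pass in 4% to 7% of runs. Among those, a drop appears in 78% to 90% as written and in 83% to 95% with the same-sample comparator.

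**7. Masking when mediation is real.** Assumptions: 48 children, total effect .45, group difference in the mediator 0.8 SD, mediator slope 0.3, about 10% of session measures missing, all in the AAI arm and concentrated in poor responders (a strong assumption). Among runs passing both steps, the comparison as written shows no drop in 15% (same outcome) to 21% (primary outcome averaging post and follow-up), against about 0% on the same sample. With random 10% gaps the figures are 1% to 4%, against 0.1%.

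**The case against.** The strongest reply is that the parenthesis in the quoted rule most naturally means the same change-score model without the mediator, which is the ordinary total-versus-direct comparison. The sentence does speak of behavioural change, defined just before as pre-post change. This stands as an ambiguity. A reader might infer that the two models certainly use different children and outcomes, but the documents never define the mediation set. The mismatch follows from a literal reading of the comparator and from the data each model needs.

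Three further points stand:

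- **The drop is not read alone.** Two significance conditions come first, and the bootstrap, Sobel and Monte Carlo estimates do not use the cross-model comparison. Under the assumptions in step 4, random gaps alone give a drop of 0.09 (20% of .45) or more in about 15% of trials (44 of 48 retained) or 27% (38 retained). It is tempting to read these as rates of false mediation findings. They are not, because they ignore both conditions and count movement in one direction only.
- **Withdrawal alone does not create the mismatch.** A child who leaves with no follow-up is in neither model. Only children with some follow-up but no session measure, or no post visit, matter. Applying the 8% attrition to the 48 would count it twice.
- **The informative patterns are assumed.** Nothing in the documents shows that missed sessions depend on outcome or arm. Participation is already to be tracked and compared between arms.

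The two conditions do not answer the masking problem: a real mediator can pass both and still show no drop under the plan's comparison.

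**Conclusion.** The point holds in limited form. As worded, the last Aim 3 step may compare coefficients from different children and different outcomes, so the drop need not equal the indirect effect. Random missingness makes it noisier. Missingness tied to outcome and arm can push it either way, including hiding a real mediator after both significance steps.

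The size cannot be taken from the documents. Under the stated assumptions, outcome-related gaps of 10% to 20% shift the mean drop by 0.08 to 0.20 SD, about 18% to 45% of an effect of .45. Weaker dependence on outcome would give less, and with random gaps the mean shift is zero.

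A reader might also infer that correcting the comparator would reduce false mediation findings. The calculations do not support this: after the two significance steps, a drop is about as common on the same sample as across models. The gain is that the reported drop agrees with the indirect effect it is meant to describe. Severity is low, because the aim is exploratory and reported with intervals.

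**What to change.** In the last step of the Aim 3 example, replace the comparator with: *a treatment-only model for the same outcome (pre-post change), fitted to the same children who have the mediator and the outcome*. Label that estimate as distinct from the Aim 1 result. State that the Aim 3 conclusion rests on the confidence interval for the indirect effect already planned, with the drop as description only.

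The cost is a sentence or two and one extra model per mediator, with no new data. The Progress Report says no data had been analysed at that renewal. The downside is that the treatment-only estimate beside each mediator will differ slightly from the Aim 1 headline, hence the label. Multiple imputation of missing session measures is optional and not part of this change.
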